## 7.3 Severe outcomes with no laboratory evidence of in utero transmission

As noted in Section 5, this may possibly represent a distinct outcome, requiring its own analysis with respect to GA at infection and other risk factors. If so, the analysis would be along the same lines as the analyses above. Alternatively, if, as we suspect, persistent antibody is found in these cases, then no special provision is required.

#### 7.4 Analysis of gestational age at maternal infection

We start with an analysis that assumes perfect test sensitivity and specificity. The gestational age at the onset of maternal infection is  $\pi_i(t)$ , t in weeks. Although the period of interest is between just before conception and delivery, ie the interval  $-2 \le t \le G_i$ ,  $\pi_i(t)$  is defined over a wider interval  $-2 - D \le t \le G_i + D$ , where D is the maximum duration of a test of persistence. This is because a first IgM+ test D weeks after delivery, or an IgM- test D+2 weeks before conception, both provide information about the probability of infection during pregnancy. Because there may be a finite probability that the maternal infection occurred before conception,  $\sum_{-2 \le t \le G_i} \pi_i(t)$  can take any value

between 0 and 1. Some special cases help clarify the concepts:

7.4.1 Onset of infection marked by symptoms. If a woman has symptoms in pregnancy starting at T then  $\pi_i(t) = 1$ , if t = T and  $\pi_i(t) = 0$ , if  $t \neq T$ .

7.4.2 Seroconversion alone. If the interval is defined by seroconversion during pregnancy, ie between a last lgG- at  $t_1$  and a first lgG+ at  $t_2$ , then in the absence of any other information,

$$\pi_i(t) = 1/(t_2 - t_1 + 1)$$
, if  $t_1 \le t \le t_2$ , else 0.

7.4.3 Surveillance data alone. Alternatively, suppose there are surveillance counts M(t) of suspected or confirmed cases (of ZIKV, DENV, or CHIKV) depending on the disease being studied [4], then the "a priori" distribution of when the infection might have occurred (given that it occurred in pregnancy) can be represented as a Dirichlet distribution:

$$\pi_i(t) = \alpha(t), \quad \alpha(t) \sim Dirichlet(M(t)), \quad -2 \le t \le G_i$$

7.4.4 PCR+ or IgM+, no surveillance data. If the specified interval is defined by a PCR+ or IgM+ test at time  $t_2$  and the earliest possible date of infection was  $t_1$  (which might be marked by an IgM- result, or  $t_1 = t_2 - D$ ) then, if the cumulative persistence distribution (the probability that persistence is d or less weeks) is  $F(d,\theta)$  with parameter(s)  $\theta$ , then (dropping the  $\theta$ ):

Author: [name] (UNIVBRIS)

20

$$\pi_i(t) = \frac{F(t_2 - t)}{\sum_{t_1 \le u \le t_2} F(u - t)}, \text{ if } -2 \le t \le t_2, \text{ else } 0$$

7.4.5 PCR+ or IgM+ with surveillance data. Now we assume the same test results, but surveillance data is available as well:

$$\pi_i(t) = \frac{\alpha(t)F(t_2 - t)}{\sum_{t_1 \le u \le t_2} \alpha(u)F(u - t)}, \text{ if } t_1 \le t \le t_2, \text{ else } 0$$

7.4.6 If the infant is congenitally infected, and we have PCR+ or IgM+ with surveillance data as above, we need only consider scenarios in which the maternal infection occurs during pregnancy. The summation in the denominator is therefore over:  $Max(t_1, -2) \le u \le Min(t_2, G_i)$ 

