#### 5.3 Gestational age (GA) at maternal infection

In a full data analysis, the target parameter here is not a single date, but a *probability distribution* for each woman, representing when the onset of infection was likely to have occurred, relative to the date of conception which may itself be imperfectly known. To simplify presentation in this SAP we represent this as a discrete distribution in units of one week. Information on the distribution of GA at infection will be derived from one or more of the following

- (a) the date of symptoms, if reported
- (b) dates of a first PCR+ test result and subsequent PCR results
- (c) seroconversion, between last IgG- and first subsequent IgG+
- (d) dates of a first IgM+ and subsequent IgM tests
- (e) dates of an initial IgG+ followed by a rising IgG titer subsequent IgG tests
- (f) avidity tests may also be used to help estimate date of infection, especially in samples that are IgM+ and/or IgG+ at recruitment

Note that an initial PCR+ or IgM+ test result is only informative about timing of infection to the extent that the population distributions of PCR persistence and IgM persistence are known. Thus, test persistence information will be critical in estimating GA at maternal infection (see *Section 7.4*).

In practice, if the tests all had perfect sensitivity and specificity, the sequence of test results would either indicate no maternal infection during pregnancy, or it would define an *interval* during which infection has occurred. The persistence distributions, if relevant, will impact on the probability distribution of GA at infection *within* that interval. The issue of test accuracy adds a further layer of complexity, discussed in the next section.

A third source of information is the weekly local surveillance of incident cases of confirmed or suspected ZIKV, DENV and CHIKV [4]. If we reasonably assume that the attack rates in the general population are proportional to attack rates in the pregnant women being recruited, the surveillance data represents an *a priori* distribution of GA at maternal infection within the interval defined by the sequence of tests. The PCR or IgM persistence distributions, if relevant, will combine with the surveillance information to define maternal GA at infection.

Author: [name] (UNIVBRIS)

16

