In order to use information on test sensitivity and specificity, we must also take into account the *absolute* risk of infection in each pregnant woman during the period when she is pregnant. A ZIKV IgM+ result is more likely to be a false positive if there are few surveillance reports of ZIKV at that time; and more likely to be a DENV infection if large numbers of DENV are being reported. Estimates of the *temporal trends* in infection of ZIKV, DENV and CHIKV are available from routine surveillance sources, as noted above; to obtain estimates of the absolute risk surveillance data must be supplemented by data on the proportion of infections, whether symptomatic or not, that are reported to the surveillance center. This proportion, which will vary between ZIKV, DENV and CHIKV, can be *approximately* estimated by aligning weekly surveillance reports with data from ZIKA-VT (See *Section 8.1*).

Following reports of sexual transmission of ZIKV, ZIKA-VT will be collecting information on infection in fathers / partners. We will explore the possibility of using this information alongside surveillance data when estimating the likely timing of maternal infection.

Author: [name] (UNIVBRIS)

**17** 

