8.1.6 Incidence of primary infections estimated by increase in seroprevalence. If we know or can estimate the cumulative incidence at a starting point T, then cumulative incidence at time t is related to incidence between t and T as follows:

$$\pi(t) = \pi(T) + (1 - \pi(T) \left( 1 - \exp\left( -\sum_{T \le u \le t} \lambda(u) \right) \right)$$

This can be modelled, for example assuming piece-wise constant incidence.

For DENV infection, which has been present for much longer, it may be preferable to model age-and time-specific cumulative incidence:

$$\pi(a,t) = \pi(a,T) + (1-\pi(a,T)\left(1-\exp\left(-\sum_{T \le u \le t} \lambda(a-T+u,u)\right)\right)$$

Using data from pregnant women, we would model incidence from time T and age 16 upwards.

These calculations assume that cumulative incidence can be estimated by adjusting seroprevalence for sensitivity and specificity as shown in *Section 8.1.2* 

8.1.7 Alignment with surveillance data: population estimates of incidence. Once estimates of incidence are available, they can be aligned with surveillance reports to estimate the proportion of incident infections (symptomatic or not) that are reported to the surveillance system. "Alignment" should be interpreted as putting the dates of the tests on the real timescale, so that incidence estimates for ZIKV, DENV, and CHIKV based on ZIKA-VT data can be compared to numbers of cases notified to national or regional surveillance centers, both confirmed and suspected.

If the estimated incidence in some period t is  $\lambda(t)$  and M(t) cases are reported in, say, the population of adult women aged 16-44, over the same time period and from the same area where ZIKA-VT is recruiting, then we can calculate the proportion of all infections that were reported over that time period as :

$$\theta(t) = \frac{M(t)}{N(1 - e^{-\lambda(t)})}$$

Where N is the relevant population size. This quantity can be examined over time to see if it remains relatively stable, and can be used in analyses of test persistence and adjustments for sensitivity and specificity needed to estimate the gestational age of maternal infection and vertical transmission rate (see Sections 5,7).

Further, once an estimate  $\theta(t)$  is available, it can be used to "gross-up" counts M(t), to estimate the true number of infections on a national or regional basis:  $M(t)/\theta(t)$ .

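### Raw weekly surveillance counts used as Dirichlet parameters (7.4.3) leave the dating prior undefined, or give a week exactly zero probability, whenever that week has no reported case

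*SAP*

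**What the plan says.** SAP section 5.3 expresses gestational age at infection on a weekly grid ("we represent this as a discrete distribution in units of one week") and brings surveillance in as a source of timing information: "A third source of information is the weekly local surveillance of incident cases". The link to the cohort is a proportionality assumption: "If we reasonably assume that the attack rates in the general population are proportional to attack rates in the pregnant women being recruited".

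Section 7.4.3 puts this into a formula. It starts "suppose there are surveillance counts M(t) of suspected or confirmed cases" and sets π_i(t) = α(t), with α(t) ~ Dirichlet(M(t)), for weeks −2 to G_i. Section 7.4.5 then weights each week by the product of α(t) and the persistence term. Section 7.4.6 keeps that product for mothers of congenitally infected infants and only narrows the weeks summed over.

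On reporting, section 5.4 says that an absolute risk requires data on "the proportion of infections, whether symptomatic or not, that are reported to the surveillance center", and 8.1.7 defines θ(t) for that purpose ("then we can calculate the proportion of all infections that were reported over that time period as").

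No section gives an offset, a minimum, a smoother or any other rule for a week in which M(t)=0.

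**The concern.** The prior fails on data that the SAP expects. A Dirichlet is defined only when all its parameters are positive, and local weekly counts of a seasonal arbovirus will include zeros. Section 8.1 stratifies by mosquito season. Section 8.2.3 plans to use stretches of more than 4 or 5 months in which surveillance shows no circulation. Appendix 7 lists the one named source by week and by parish or region.

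If the software does not simply stop, the limiting form treats a week without reports as a week in which infection could not have happened. That contradicts the SAP's own account of under-reporting. It also lets surveillance silence overrule laboratory evidence.

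What is at stake is π_i(t). It feeds V(t) in 7.1, C(t) in 7.2, the persistence likelihood in 7.5.1 and the month or trimester probabilities carried forward in 7.7.

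**Working it through.** The SAP states no figure on this point, so there is none to reproduce. The check has four steps. Every count, curve and reporting fraction below is an assumption, because the SAP gives none.

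**1. The distribution.** For Dirichlet(M), E[α(t)] = M(t)/ΣM, and all M(t) must exceed 0. Take 12 weekly counts 0, 0, 1, 0, 2, 5, 12, 20, 9, 3, 1, 0, with sum 53.
- As written: standard software rejects the vector because some parameters are zero.
- In the limit as the zero parameters shrink to 0: in 200,000 draws the four zero-count weeks have mean 0 and maximum 0.
- A week with one report has mean 1/53 = 0.019 (95% interval 0.0005 to 0.069). It is improbable but possible.

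**2. Combination with a test, as in 7.4.5.** Put a positive test in week 12, a zero-count week. Assume the probability of still testing positive d weeks after infection is S(d) = exp(−(d/2)^1.5). Then S(0)=1, Σ S = 2.315 and Σ M·S = 4.683 over the 12 weeks. With offset c, the probability of infection in week 12 is c/(4.683 + 2.315c):
- c = 0: 0/4.683 = 0
- c = 0.5: 0.5/5.840 = 0.086
- c = 1: 1/6.998 = 0.143

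The zero at c = 0 holds for any persistence curve, because α(t) is a factor. If every week in the interval has M = 0, numerator and denominator are both 0. The choice of c matters, so it should be fixed in advance.

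**3. Zero reports with real infections.** With n infections in a week and reporting fraction θ, P(M=0) = (1−θ)^n:
- n = 5: 0.95 at θ = 0.01, 0.33 at θ = 0.20
- n = 20: 0.82 at θ = 0.01, 0.01 at θ = 0.20
- n = 100: 0.37 at θ = 0.01, below 0.001 at θ = 0.20

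**4. How often it could bite.** Assume one wave over weeks −2 to 40 (43 weeks), with p(t) proportional to exp(−(t−20)²/72) + 0.1. This is a peak at week 20, SD 6 weeks and a baseline one tenth of the peak term. With R reports in total and Poisson counts of mean R·p(t), the share of infections falling in zero-count weeks is Σ p(t)·exp(−R·p(t)). The chance that a 5-week interval at either edge of the window is all zeros is exp(−R·Σp) over those five weeks.

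| Total reports R | Infections in zero-count weeks | Edge interval all zero |
|---|---|---|
| 20 | 50% | 56–58% |
| 40 | 29% | 31–34% |
| 80 | 13% | 10–11% |
| 200 | 4% | 0.3–0.4% |
| 1,000 | 0.02% | about 0% |

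At least one of the 43 weeks is zero with probability 1 − Π(1 − exp(−R·p(t))). That is above 99% for R from 20 to 200, and about 4% at 1,000.

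**The case against.** The best defence is that 7.4 is expository. It assumes perfect tests and introduces its formulas with "Some special cases help clarify the concepts", and the accuracy-adjusted calculation in 7.6 and Appendix 2 uses an absolute incidence λ(t) instead of Dirichlet(M(t)). This stands in part. In Appendix 2 the (1 − Sp) term keeps the denominator positive when Sp < 1, so 0/0 does not arise there, and 8.1.6 allows piecewise-constant incidence, which is a form of smoothing. But 7.4.5 and 7.4.6 are the only places where relative surveillance timing is combined with test results, and Appendix 2 describes its own formula as an expansion of 7.4.5. If λ(t) is obtained by inverting 8.1.7 with a fixed θ, then λ(t) = −ln(1 − M(t)/(Nθ)), which is 0 when M(t) = 0, and the same problem returns.

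A second defence is that the SAP intends quiet surveillance to count against an IgM-positive result (5.4, 8.2.3). That is so for long quiet periods. But 8.2.3 regards such results as very probably false positives, not certainly so, and short gaps between reports are not covered by that reasoning.

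A third is that counts may be large. M(t) includes suspected cases, recruitment favours higher-incidence areas and periods, and the level of aggregation is open. This stands: at 1,000 reports the problem all but disappears under the assumed curve.

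Lastly, V(t) will be smoothed and later analyses use months or trimesters, so isolated zero weeks may shift little. That is plausible, and no bias in V(t) has been calculated here.

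**Conclusion.** The point holds for zero-count weeks in the surveillance-based cases 7.4.3, 7.4.5 and 7.4.6. There the stated prior is undefined, or rules out a week that test evidence cannot restore, against the SAP's own premise of incomplete reporting. The algebra needs no assumption. The frequency rests wholly on assumed counts and an assumed epidemic curve: from about half of infections at 20 reports to practically none at 1,000.

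Three stronger readings are tempting and are not supported.
- A reader might infer that weeks with few reports are also excluded. They are not: any week with M(t) ≥ 1 keeps positive probability.
- A reader might infer that the whole dating model fails. Section 7.4.1 ("If a woman has symptoms in pregnancy starting at T then" all probability goes to week T), seroconversion alone (7.4.2) and tests without surveillance (7.4.4) do not use M(t).
- A reader might infer that the sixth property claimed in section 4 is broken, or that transmission estimates are shown to be biased. That property concerns whether centers have surveillance data, not how sparse the data are, and the percentages above are shares of infections, not bias in V(t) or C(t).

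**What to change.** In 7.4.3, replace Dirichlet(M(t)) with one of two options:
- Dirichlet(M(t) + c), with c > 0 fixed in advance and results shown for a range of c; or
- α(t) proportional to a smoothed incidence λ(t), for example using the log-scale random walk that 7.5.2 already names for the persistence hazard.

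Carry the chosen form into 7.4.5 and 7.4.6. State that the same handling applies if λ(t) for Appendix 2 is derived from weekly counts through 8.1.7.

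The cost is a few lines of SAP text, a small modelling step if smoothing is chosen, and one additional sensitivity run. No data collection changes.

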#### 7.7 How the full analysis will be used

The various components discussed above can be assembled into a single analysis, as shown by the influence diagram (*Figure 1*), providing a single integrated analysis of: test persistence and its covariates; GA at maternal infection; VTR and its risk factors; and risk of severe congenital outcomes and its risk factors.

One of the outputs will be the distribution of maternal GA at infection, in weeks. We will extract the posterior mean probability that a maternal infection occurred during each month, or trimester, and take this forward to be used in analyses along the lines of Tables 3 and 4. In effect the 0,1 "dummy covariates" that would be used in conventional analyses of GA at infection as a risk factor, can then be replaced by a set of probabilities. Note that these cannot exceed one, but they need not add to one, if there is a finite probability that the infection occurred before, or after, pregnancy. Standard

Author: [name] (UNIVBRIS)

25

statistical software can then be used to explore GA at infection as a risk factor, or interactions between GA at age of infection and other risk factors, exactly as if 0,1 covariates were being used.

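### The surveillance prior α(t) is given only for weeks in pregnancy (7.4.3), but 7.4.5 uses it over an interval that can extend outside pregnancy; the support stated in 7.4.4 also conflicts with its own t₁

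*SAP*

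**What the plan says.** Section 7.4 states that πᵢ(t) "is defined over a wider interval" than pregnancy, namely −2−D to Gᵢ+D, where D is the maximum duration of test persistence. "Because there may be a finite probability that the maternal infection occurred before conception", its sum over weeks −2 to Gᵢ may take any value from 0 to 1. Section 7.7 repeats this for the trimester probabilities: they cannot exceed one, "but they need not add to one, if there is a finite probability that the infection occurred before, or after, pregnancy".

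The formulas follow as illustrations ("Some special cases help clarify the concepts"). In 7.4.3, with surveillance data alone, the a priori "distribution of when the infection might have occurred (given that it occurred in pregnancy) can be represented as a Dirichlet distribution", with range −2 ≤ t ≤ Gᵢ. In 7.4.4, for a PCR+ or IgM+ at t₂ without surveillance data, t₁ is the earliest possible date of infection and may be t₂−D. Section 7.4.5 adds the prior ("Now we assume the same test results, but surveillance data is available as well") and applies α(t) on t₁ ≤ t ≤ t₂. Section 7.4.6 cuts the sum to pregnancy when the infant is congenitally infected, because then "we need only consider scenarios in which the maternal infection occurs during pregnancy".

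**The concern.** The formula in 7.4.5 needs α(t) in weeks where the plan supplies none. A programmer who takes the only α on offer may treat the missing weeks as zero. Under 7.1, vertical transmission requires onset between week −2 and Gᵢ. A woman infected before that window or after delivery would then count in full towards the VTR, although her child cannot be vertically infected. The estimate falls, mostly for infection placed early in pregnancy. Section 1.3 calls the VTR the most important target parameter. The size of the effect would also depend on when IgM is first tested, whereas section 4 promises unbiased estimates whatever the test schedule.

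**Working it through.** **Ranges side by side**

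| SAP section | Quantity | Range of weeks |
|---|---|---|
| 7.4 | πᵢ(t) | −2−D to Gᵢ+D |
| 7.4.3 | α(t) | −2 to Gᵢ, given infection in pregnancy |
| 7.4.4 | πᵢ(t), no surveillance | −2 to t₂, else 0; denominator summed over t₁ to t₂ |
| 7.4.5 | πᵢ(t), with α(t) | t₁ to t₂; t₁ may be t₂−D |
| 7.4.6 | sum, infected infant only | max(t₁, −2) to min(t₂, Gᵢ) |

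**Section 7.4.5.** If t₁ ≥ −2 and t₂ ≤ Gᵢ, the 7.4.3 range is enough and nothing changes. If t₁ < −2 or t₂ > Gᵢ, α is undefined for some weeks. The cut in 7.4.6 would be redundant if α were already zero outside pregnancy, so 7.4.5 must intend a wider α than 7.4.3 provides.

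**Section 7.4.4.** Two cases conflict with t₁.
- t₁ > −2: with IgM− at week 8 and IgM+ at week 16, the ten weeks −2 to 7 are excluded by the negative test but stay inside the stated support.
- t₁ < −2: weeks t₁ to −3 are set to zero, although 7.4 allows them. The denominator still runs from t₁, so the dilution described for 7.4.5 does not arise here, but those weeks drop out of πᵢ(t).

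**Size under a zero reading.** The SAP gives no figure to reproduce. Its one input is IgM persistence of about 12 weeks (5.4, 8.2.3). Assumed here: 12 weeks is the mean, persistence is Weibull with shape k = 1 to 2, D = 26 to 52 weeks, and incidence is flat.

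- Weight: w(t) = α(t)·S(t₂−t), with S(d) = exp(−(d/b)^k) and b = 12/Γ(1+1/k).
- Pre-conception share = sum of w over t₂−D ≤ t < −2, divided by the sum over t₂−D ≤ t ≤ t₂.

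S is the probability that the marker still persists. The SAP's formulas print the cumulative F instead, which is a separate matter.

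Worked case, t₂ = 10, D = 52:
- k = 1: 4.08/12.36 = 33%
- k = 2: 2.30/12.50 = 18%
- Pre-conception incidence halved: 2.04/(2.04+8.27) = 20% and 1.15/(1.15+10.20) = 10%
- Pre-conception incidence doubled: 8.16/(8.16+8.27) = 50% and 4.60/(4.60+10.20) = 31%

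Flat incidence, across k and D:

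| Week of lone IgM+ | Pre-conception share |
|---|---|
| 6 | 36–47% |
| 10 | 18–33% |
| 14 | 8–23% |
| 20 | 1–14% |
| 30 | 0–5% |

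After delivery: with IgM− at week 34, delivery at week 38 and IgM+ at week 44, weeks 39 to 44 hold 62–66% of the probability.

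**Effect on VTR in such a group.** With constant V, the true transmission probability is V × (1 − share), while the zero reading models it as V. The fitted rate is therefore V × (1 − share). For an assumed V of 20% and a lone IgM+ at week 10, that is 20% × 0.67 = 13.4% to 20% × 0.82 = 16.4%.

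**The case against.** The strongest reply is that this is a gap in notation and that the plan's intention is clear. Section 7.4.3 is openly conditional and coherent by itself; only the reuse of its symbol causes trouble. Nowhere is α stated to be zero outside pregnancy, and 7.4, 7.4.5, 7.4.6 and 7.7 all point the other way. This stands. A reader might infer that the plan gives infections outside pregnancy probability zero, so that the VTR is biased as planned. The documents do not support that: α is undefined there, and the dilution is a risk of a literal implementation.

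The reach is also limited. Women dated by symptoms follow 7.4.1. Section 7.5.3 provides for PCR on all IgM+ women, and 5.3 proposes avidity tests, especially for samples already positive at recruitment. The SAP gives no figure for how many women are IgM+ when first tested. Section 8.1 says recruitment favours periods of higher incidence, which makes the halved pre-conception incidence at least plausible.

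Section 5.4 says that IgM from an infection many months before pregnancy might be regarded as a diagnostic false positive, and Appendix A2.1 has a (1−Sp) term that could absorb part of the problem. This helps only partly. Section 7.6 makes the accuracy adjustment conditional on need. A single specificity would also have to stand for a share that moves from 36–47% at week 6 to 1–14% at week 20.

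None of this supplies the α that 7.4.5 needs, or reconciles 7.4.4 with its own t₁.

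**Conclusion.** The ranges are wrong as written and need correcting. α(t) is not specified over the interval on which 7.4.5 uses it, and the support in 7.4.4 contradicts both its own t₁ and the wider interval in 7.4.

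Dilution of the VTR follows only if α is read as zero outside pregnancy, and then only for women with t₁ < −2 or t₂ > Gᵢ. It matters mainly for a lone IgM+ early in pregnancy or a first IgM+ after delivery, and little for a lone IgM+ late in pregnancy. The percentages rest on the assumed incidence, persistence shape and D, and apply to those subgroups; no effect on the overall VTR has been calculated.

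Two wider readings are not supported. One is that every IgM+ woman is affected. The other is that 5.3 itself sets a wider interval: it only calls surveillance the a priori "distribution of GA at maternal infection within the interval defined by the sequence of tests", and the wider range comes from 7.4.

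**What to change.** - For use in 7.4.5, define α(t) from M(t) over −2−D ≤ t ≤ Gᵢ+D, without the condition that infection occurred in pregnancy, wherever surveillance counts exist for those weeks. Section 7.4.3 can stay as a conditional special case if it is labelled as such and its α is given a different symbol.
- State the support as t₁ ≤ t ≤ t₂ in both 7.4.4 and 7.4.5.
- Restrict to pregnancy only through 7.1 and, for infected infants, 7.4.6.

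This follows the plan's own 7.4, 7.4.6 and 7.7 and should be settled before programming. The cost is wording and a longer surveillance extract. The extra weeks may not be available at every centre: Appendix 7 names one source so far, and section 4 expects availability to differ. Where counts are missing, the SAP should say what incidence is assumed for those weeks.
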